10.8 Blood and Urine Sample

A blood sample (34 mls (approximately 2 tablespoons)) and a urine sample will be taken at baseline, 12 weeks (and 16 weeks if the macular oedema resolved at week 12). The urine sample and part of the blood sample will be used to test for the following:

- Pregnancy Test
- Full blood cell count
- CBC with reticulocytes
- HbA1c
- Glucose
- Lipid profile (HDL, LDL, triglycerides)
- C peptide levels
- Creatinine clearance
- Albumin excretion rate
- Liver function test (ALT and AST)

10.9 Research Samples/Exploratory Analysis

The remaining part of the blood sample (10.8 above), will be used to test for ARA 290 antibodies and to complete an exploratory analysis to determine levels of inflammatory markers and carbamylated and glycosylated albumin.

The blood sample will be taken prior to ARA 290 administration at baseline, and at least 2 hours after the most recent treatment. Within 30 minutes after collection, the sample will be centrifuged at 3000 rpm for 10 minutes at 4°C. The collected serum will be transferred to transport tubes [2 tubes for ARA 290 antibodies (approximately 0.5 mL per tube), 2 tubes for carbamylated albumin, 2 tubes for glycosylated albumin, and 2 tubes for immune markers (approximately 0.1 mL per tube)] and stored at -80°C.

Patients leaving the study before study completion (i.e. week 12) will have a full evaluation like that being undertaken at the 12 week visit, unless the patient refuses consent for this evaluation to be undertaken.

10.9.1 ARA 290-Antibodies

After the last subject has the week 12 blood sample taken, one of the samples (0.5ml) of serum collected will be shipped on dry ice or liquid nitrogen via courier to The Charles River Laboratory in Montreal, Canada for analysis. The additional sample (0.5ml) of serum will be stored at the research center as back-up. The samples will be stored under code, which can be linked to subject's identity only by authorised personnel.

10.9.2 Inflammatory Biomarkers

A multiplex assay will be carried out to determine the presence of inflammatory biomarkers. Proseek Multiplex Inflammation assay is a proprietary (Olink Biosciences) methodology employing proximity extension assay technology to measure simultaneously 92 inflammation biomarkers. The volume of serum required for this purpose is 90 microliters. Details on this assay are available at www.olink.com

After the last subject has the week 12 sample taken, one of the samples (0.1ml) of serum collected will be shipped on dry ice or liquid nitrogen via courier to an appropriate laboratory for analysis. The additional sample (0.1 ml) of serum will be stored at the research center as back-up. The samples will be stored under code, which can be linked to subject's identity only by authorised personnel.

10.9.3 Carbamylated and Glycosylated Albumin

An assay will be carried out to determine levels of carbamylated albumin a measure of renal function and metabolic status and of glycosylated albumin, a marker of glucose control. After the last subject has the week 12 sample taken, one of the samples (0.1ml) of serum for each of the above (i.e. 0.1 ml of serum for the purpose of determining carbamylated albumin and 0.1 ml for serum for glycosylated albumin) collected will be shipped on dry ice or liquid nitrogen via courier to an appropriate laboratory for analysis. The additional sample (0.2 ml) of serum will be stored at the research center as back-up, in 2 x 0.1 ml aliquots. The samples will be stored under code, which can be linked to subject's identity only by authorised personnel.

On completion of the sample analysis and transfer of this to the CTU, all samples sent to the laboratories will be destroyed and confirmation of destruction will be sent to the CTU. On receipt of this confirmation, the CTU will confirm with the PI, at which point all back up samples will also be destroyed and confirmation of destruction will be sent to the CTU.

10.10 Telephone Checks

The PI or designee will contact the patient by telephone 2 weeks post enrolment onto the study to check compliance with study drug administration and to assess if the patient is experiencing any adverse events.

For those patients who withdraw from the trial/study drug prior to 12 weeks or following the completion of 12 weeks of treatment (and who do not need to attend the 16 week visit), the PI or designee will contact the patient by telephone 4 weeks post study drug termination to assess if the patient is experiencing any adverse events.

11. DATA COLLECTION & MANAGEMENT

11.1 Data Quality

Data integrity and study credibility depend on factors such as ensuring adherence to the protocol and using quality control measures to establish and maintain high standards for data quality.

The Chief Investigator (CI) and CTU will provide training to site staff on trial processes and procedures including the CRF and data collection.

On-site monitoring visits during the trial will check the accuracy of entries on CRF's against the source documents, the adherence to the protocol, procedures and Good Clinical Practice (GCP).

Quality control is implemented by the CTU in the form of Standard Operating Procedures (SOPs), which are defined to encompass aspects of the clinical data management process, and to ensure standardisation and adherence to International Conference of Harmonisation Good

Clinical Practice (ICH-GCP) guidelines and regulatory requirements.

Data quality control checks will be carried out by the Data Manager to ensure 100% accuracy and data errors will be documented in Quality Control Reports with corrective actions implemented.

Data validation will be implemented and discrepancy reports will be generated following data entry to identify discrepancies such as out of range, inconsistencies or protocol deviations based on data validation checks programmed in the clinical trial database.

A Data Monitoring & Ethics Committee (DMEC) will be convened for the study to carry out reviews of the study data at staged intervals during the study.

11.2 Data Collection

To ensure accurate, completed and reliable data are collected, the CTU will provide training to site staff in the format of investigator meetings and/or site initiation visits.

All data for an individual patient will be collected by the PI or designee and recorded in the CRF or questionnaires for the study. Patient identification on the CRF and questionnaires will be through their unique trial identifier, allocated at the time of recruitment, and patient initials. Data will be collected and recorded on the CRF by the PI or designee and the patient will complete the questionnaires from the time the patient is considered for entry into the trial through to their 12 week follow up, (or 16 week if at the 12 week follow up visit the patient's retina is dry).

CRFs and questionnaires are to be submitted to the CTU as per the CRF Submission Schedule, along with a CRF Tracking Form.

11.3 Data Management

Following the submission of CRFs and questionnaires to the CTU, the data will be processed as per the CTU Standard Operating Procedures (SOPs). Data queries will be generated for site staff as required to clarify data or request missing information. The designated site staff will be required to respond to these queries and send them back to the CTU after they have been reviewed and signed by the PI or designee. Any amended information will then be entered in the study database. A copy of the signed data query form should be retained with the CRF at the investigator site.

12. STATISTICAL CONSIDERATIONS

12.1 Sample Size

This will be an early phase, open label, interventional pilot study to evaluate the potential beneficial effect of ARA 290 for the treatment of patients with DR and DMO and further assess the safety of this treatment. Ten patients will be recruited. A sample of this size is expected to be sufficient to provide an indication of a potential beneficial effect of the drug on the outcomes investigated and further information on safety of ARA 290 in a diabetic population. Data obtained in this study will be used to inform future larger studies.

12.2 Data Analysis

In participants in whom both eyes are eligible for inclusion into the study, the eye with the better BCVA will be used as the study eye; however data will be collected and evaluated for both eyes.

Given the short time course of the study (12 weeks), drop outs are not expected to occur.

12.3 Statistical Methods

Descriptive statistics will be used for the evaluation of primary and secondary outcomes. Differences in mean (SD) for all the continuous variables investigated including visual acuity, central subfield thickness, area of retinal ischaemia, retinal sensitivity, patient reported outcome scores as well as levels of ARA 290 antibodies. Adverse events will be presented using counts and percentages. Additionally, the % of participants with 10 or more and 15 or more ETDRS letter gain will be also reported. Data obtained at week 16 will be similarly evaluated. Exploratory analysis in relation to inflammatory markers and carbamylated and glycosylated albumin will also be observed from baseline to the week 12 visit. A Statistical Analysis Plan (SAP) will be created by the Trial Statistician, reviewed by the DMEC and approved by the CI.

12.4 Missing Data

As the analysis is only descriptive, no imputation or sensitivity analysis will be performed.

13.1 Definition of Adverse Events

The European Clinical Trials Directive 2001/20/EC and applicable clinical trial regulations set out the legal requirements for adverse event recording, management and reporting of clinical trials.

Term Definitions for Adverse Events				
Adverse Event (AE)	Any untoward medical occurrence in a participant to whom a medicinal product has been administered, including occurrences which are not necessarily caused by or related to that product.			
Adverse Reaction (AR)	Any untoward and unintended response in a participant to an investigational medicinal product, which is related to any dose administered to that participant.			
Unexpected Adverse Reaction (UAR)	 An adverse reaction, the nature and severity of which is not consistent with the information about the medicinal product in question set out in: The Summary of Product Characteristics (SmPC) for that product (for products with a marketing authorisation) or The Investigator's Brochure (IB) relating to the trial in question (for any other investigational product) 			
Serious Adverse Event (SAE)	 A SAE is an adverse event that: results in death is life-threatening requires hospitalisation or prolongation of existing hospitalisation* results in persistent or significant disability or incapacity consists of a congenital anomaly or birth defect is any other important medical event (s) that carries a real, not hypothetical, risk of one of the outcomes above. 			
Serious Adverse Reaction (SAR)	 A SAR is an adverse reaction that is classed as serious and which is consistent with the information about the investigational medicinal product in question set out in the: SmPC in the case of a licensed product. IB for any other investigational product. 			
Suspected unexpected Serious Adverse Reaction (SUSAR)	 A SUSAR is a serious adverse reaction which is unexpected i.e. the nature and severity of which is not consistent with the information about the medicinal product in question set out: in the case of a product with a marketing authorisation, in the SmPC for that product in the case of any other investigational medicinal product, in the IB relating to the trial in question. 			

Table 3: Terms and Definitions for Adverse Events

*Hospitalisation is defined as an inpatient admission regardless of length of stay, even if the hospitalisation is a precautionary measure for continued observation. Hospitalisations for a pre-existing condition, including elective procedures that have not worsened, do not constitute a SAE.

13.2 Eliciting Adverse Event Information

The PI or designee will record all directly observed AEs and all AEs spontaneously reported by the patient. In addition, the patient will be asked about AEs at each visit following initiation of treatment. The PI or designee must assess all AEs for seriousness, causality, severity and if the adverse event is related to the study drug for expectedness.

13.3 Assessment of Seriousness

The PI or designee should make an assessment of seriousness i.e. is this is an adverse event, adverse reaction or suspected unexpected adverse reaction that:

- Resulted in death
- Is life-threatening
- Requires hospitalisation or prolongation of existing hospitalisation
- Results in persistent or significant disability or incapacity
- Consists of a congenital anomaly or birth defect
- Is any other important medical event(s) that carries a real, not hypothetical, risk of one of the outcomes above

13.4 Assessment of Causality

The PI or designee should make an assessment of causality, i.e. the extent to which it is believed that the event may be related to the study drug:

- Not Related: Temporal relationship of the onset of the event, relative to administration of the product, is not reasonable or another cause can by itself explain the occurrence of the event.
- **Unlikely:** Temporal relationship of the onset of the event, relative to administration of the product, is likely to have another cause which can by itself explain the occurrence of the event.
- **Possibly*:** Temporal relationship of the onset of the event, relative to administration of the product, is reasonable but the event could have been due to another, equally likely cause.
- **Probably*:** Temporal relationship of the onset of the event, relative to the administration of the product, is reasonable and the event is more likely explained by the product than any other cause.
- **Definitely*:** Temporal relationship of the onset, relative to administration of the product, is reasonable and there is no other cause to explain the event, or a re-challenge (if feasible) is positive.

* Where an event is assessed as possibly, probably or definitely related, the event is an AR.

13.5 Assessment of Severity

The PI or designee should make an assessment of severity for each AE according to the following categories:

- **Mild (Grade 1):** A reaction that is easily tolerated by the trial participant, causing minimal discomfort and not interfering with every day activities.
- **Moderate (Grade 2):** A reaction that is sufficiently discomforting to interfere with normal everyday activities.
- Severe (Grade 3): A reaction that prevents normal everyday activities.
- Life Threatening (Grade 4): A reaction that has life threatening consequences; urgent intervention indicated.
- Death (Grade 5): A reaction that results in death.

13.6 Assessment of Expectedness

The PI or designee is required to make an assessment of expectedness based on any relevant product information as documented in the IB. Adverse reactions or serious adverse reactions may be classed as either

- **Expected:** The AR is consistent with the toxicity of the study drug listed in the IB.
- Unexpected: The AR is not consistent with the toxicity in the IB.

An AR may be described as 'unexpected' if it has occurred with greater frequency or severity that might otherwise have been expected.

13.7 Adverse Event Reporting Period

The AE reporting period for the trial begins upon enrolment into the trial and ends 30 days following the last administration of the study drug. All AEs assessed by the PI as possibly, probably or definitely related to the study drug and all SAEs that occur during this time will be followed until they are resolved or are clearly determined to be due to a patient's stable or chronic condition or intercurrent illness(es).

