8.4 Withdrawal of Consent

Patients may withdraw or be withdrawn from the trial at any time without prejudice. In the event of consent withdrawal, patients will be asked for their permission to use the data already collected to date. If this permission is declined, then any data collected to date on that patient will not be entered into the trial analysis.

If the patient and/or PI request termination of the trial drug during the treatment period, the drug will be stopped and the patient will revert to standard care treatment. The patient will be advised that if any event occurs within 28 days of receiving the last dose of the study drug, which the patient considers might be related to the study drug, the patient should contact the clinic to discuss with the PI.

As an additional safeguard, the PI or designee will contact the patient by telephone 4 weeks post study drug termination to assess if the patient has experienced any adverse events.

If a patient withdraws or is withdrawn from the trial they will be offered the standard care treatment which is currently anti VEGF drugs within the National Health Service (NHS).

Withdrawal of consent, or patient/PI request to terminate the study drug, will be recorded on the Case Report Form (CRF).

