10. PARTICIPANT TIMELINE: SCHEDULE OF ASSESSMENT AND DATA COLLECTION

10.1 Schedule of Assessments

All patients must be evaluated during the study according to the schedule of assessments outlined in Table 2.

Table 2: Schedule of Assessments

	Screening/ Baseline	2 weeks	4 weeks	8 weeks	12 weeks	16 weeks*	4 weeks post drug termination**
Consent	✓						
Pregnancy Test	√						
Medical History	✓		√	✓	√	✓	
Medications	✓		✓	√	√	✓	
Vital Signs***	✓		✓	√	✓	√	
Distance Visual Acuity	✓		✓	✓	✓	✓	
Microperimetry	 ✓ 				✓	✓	
Schirmer Test	✓				✓	✓	
SD-OCT	 ✓ 		✓	✓	✓	✓	
Wide-angle FFA	✓				✓		
Blood sample for ARA 290 antibodies, immune markers, carbamylated and glycosylated albumin	✓				✓		
Blood sample for full blood cell count	√				√	√	
Liver function test (LFT)	 ✓ 				~	✓	
Urine Sample	✓				✓	✓	
Adverse Events		~	~	~	~	✓	✓
VFQ-25	~				~	✓	
EQ-5D-5L	 ✓ 				~	✓	
C-SSRS	~		~	√	~	✓	
Telephone check		✓					 ✓

* 16 week visit will take place only if the retina is found to be dried and the DMO has resolved at week 12

** 4 week post study drug termination telephone check will be completed for patients who withdraw from the trial/study drug prior to 12 weeks, or at 12 weeks, and who do not need to attend the 16 week visit.

 *** Vital signs: height (first visit only); weight; heart rate; temperature; blood pressure, oxygen saturation, BMI

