13.11 Pregnancy

13.11.1 Contraceptive Advice

While ARA 290 has not been shown to adversely affect pregnancy or harm the fetus in two animal studies, it is an investigational drug and therefore pregnant or breast feeding women will be excluded from the study. A pregnancy test will be performed in every woman of child-bearing age before she is included into the study. All non-pregnant women of child-bearing age will be instructed at the beginning of the study, before receiving the study drug, that it is essential that they use effective contraception to prevent pregnancy e.g. oral contraceptive and condom, intra-uterine device (IUD) and condom, diaphragm with spermicide and condom. This contraceptive should be continued for at least 30 days post administration of the final dose of the study drug. Women who refuse to take effective contraception will not be permitted to enter the study, and women who stop using effective contraception during the course of the study will be discontinued from study participation.

Male study participants will be advised that they should not father a child during this study and for a safety period of 30 days after final treatment. To ensure this, male participants will be advised that they or their partner must use reliable forms of contraceptive during the trial and for 30 days afterwards, e.g. oral contraceptive and condom, intra-uterine device (IUD) and condom, diaphragm with spermicide and condom.

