13.11.2 Pregnancy Reporting

Women who become pregnant during the study should stop ARA 290 immediately and inform the PI. Male study participants should inform the PI if their partner becomes pregnant while he is in the study. Pregnancy is not considered an AE or SAE, however an abnormal outcome would be. Therefore the PI or designee must collect pregnancy information for female participants, and for females who become pregnant while their partners are participating in the trial. Consent should be obtained to follow up the pregnancy from the female partners of male participants.

The pregnancy reporting period for the trial is from the commencement of the study drug until 30 days post admin of the final dose of study drug. The PI or designee should complete and submit the Pregnancy Reporting Form to the CTU by email within 14 days of being made aware of the pregnancy. The CTU will acknowledge receipt of the Pregnancy Reporting Form within two working days by email to the site.

Any pregnancy that occurs in a participant or participant's partner during the trial should be followed to outcome. Follow up/outcome information should be provided to the CTU as soon as it becomes available. Araim Pharmaceuticals, Inc. may also request their consent to collect confidential information about their health and that of the baby.

An unwillingness to undertake adequate precautions to prevent pregnancy for the duration of the trial is an exclusion criteria for this study.

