3.2 Data completion schedule

The following table describes the time points for completion of clinical record forms.

Table 1. Data Completion Schedule

	Screening / Baseline	2 week s	4 weeks	8 weeks	12 weeks	16 weeks*	4 weeks post drug termination**
Consent	✓						
Pregnancy Test	✓						
Medical History	✓		√	√	√	✓	
Medications	✓		√	√	√	✓	
Vital Signs***	✓		√	√	√	√	
Distance Visual Acuity	✓		√	√	✓	√	
Microperimetry	√				✓	√	
Schirmer Test	√				✓	√	
SD-OCT	√		✓	✓	✓	✓	
Wide-angle FFA	✓				✓		
Blood sample for ARA 290 antibodies, immune markers, carbamylated and glycosylated albumin	✓				✓		
Blood sample for full blood cell count	~				√	✓	
Liver function test (LFT)	~				✓	√	
Urine Sample	✓				✓	✓	
Adverse Events		✓	√	✓	✓	√	✓
VFQ-25	~				✓	√	
EQ-5D-5L	~				✓	√	
C-SSRS	~		✓	✓	✓	√	
Telephone check		√					✓

- * 16 week visit will take place only if the retina is found to be dried and the DMO has resolved at week 12
- ** 4 week post study drug termination telephone check will be completed for patients who withdraw from the trial/study drug prior to 12 weeks, or at 12 weeks, and who do not need to attend the 16 week visit.
- *** Vital signs: height (first visit only); weight; heart rate; temperature; blood pressure, oxygen saturation, BMI

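### AEs are reportable to 30 days after the last dose, but the last planned safety call is at 4 weeks, so active AE questioning nominally stops about two days short

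*Protocol*

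**What the plan says.** Protocol 13.7 opens AE reporting at enrolment, and the period "ends 30 days following the last administration of the study drug". Two neighbouring sections use the same 30 days: contraception is to be "continued for at least 30 days post administration of the final dose of the study drug" (13.11.1), and the pregnancy reporting period runs "until 30 days post admin of the final dose of study drug" (13.11.2).

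The contact schedule uses a different figure. Under Protocol 10.10 the site is to "contact the patient by telephone 4 weeks post study drug termination". Protocol 8.4 provides for the same call, and the footnotes to Protocol Table 2 ("4 week post study drug termination telephone check will be completed") and SAP Table 1 ("4 week post study drug termination telephone check will be completed for patients who withdraw") repeat the timing. The call is for patients who stop early and for those who finish 12 weeks without needing a week-16 visit. None of these places gives a window for it.

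Protocol 8.4 also advises patients whose drug is stopped during treatment to contact the clinic "if any event occurs within 28 days of receiving the last dose of the study drug", where they think the event might be related to the drug.

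On how AEs are collected, Protocol 13.2 states: "The PI or designee will record all directly observed AEs and all AEs spontaneously reported by the patient". It adds that patients are asked about AEs at each visit after treatment starts.

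**The concern.** The reporting period and the contact schedule do not end together. Up to the final call, AEs are actively asked about. From then to day 30 they are still reportable, but nothing is planned to find them, so capture depends on direct observation or on the patient volunteering the event. Patients who stop early are also given a 28-day limit in 8.4, which is shorter than the period in which their events count.

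Further safety information is a stated purpose of the study (Protocol 12.1), and 84 days of dosing is longer than the 28 days used in most previous studies (Protocol 3.3). SAP 7.5 lists the AE counts without saying how far active questioning ran. A reader of the report could take the whole 30-day period as having been collected in one way.

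**Working it through.** The 30 days is a definition with no calculation behind it, so there is no figure to reproduce. The check is day arithmetic.

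**Inputs**

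| Input | Value | Source |
|---|---|---|
| End of AE reporting | day 30 after last dose | Protocol 13.7 |
| Final telephone check | 4 weeks after stopping the drug, no window | Protocol 8.4, 10.10, Table 2; SAP Table 1 |
| Dosing period | 84 days | Protocol 9.5 |
| Patients | 10 | Protocol 12.1; SAP 5 |
| Week-16 visits needed | none | SAP 6 |

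**Nominal gap**, taking stopping the drug to mean the last dose:

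- Day of call: 4 x 7 = 28.
- Gap per patient: max(0, 30 - day of call) = 30 - 28 = 2 days.
- Share of the post-dose reporting period: 2/30 = 6.7%.
- Share of the time from first dose to the end of reporting: 84 + 30 = 114 days, and 2/114 = 1.8%.
- Across the trial: 10 x 2 = 20 patient-days.

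**If a window applied to the call.** None is stated, so these rows are assumptions. The +/- 2 days is borrowed from the drug-supply text on study visits (Protocol 9.2), and the +/- 7 days from the week-12 outcomes (Protocol 6.1).

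| Assumed window | Call falls on | Gap per patient | Over 10 patients |
|---|---|---|---|
| none | day 28 | 2 days | 20 patient-days |
| +/- 2 days | day 26 to 30 | 4 to 0 days | 40 to 0 patient-days |
| +/- 7 days | day 21 to 35 | 9 to 0 days | 90 to 0 patient-days |

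The upper ends require every patient to be called at the earliest permitted day. A window centred on day 28 can lengthen the gap as well as close it.

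**Would the week-16 visit have closed the gap?** Counting the first dose as day 0, the visit is at 16 x 7 = day 112. With the last dose on day 83, it falls 112 - 83 = 29 days later and leaves 1 day. With the last dose on day 84, it falls 28 days later and leaves 2 days. It would not have reached day 30 under either count, and no patient needed it.

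**After the change.** A call on day 30 or later gives a gap of 0.

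**The case against.** The strongest reply is that nothing in the plan is contradictory. Section 13.7 defines which events count, 10.10 sets when staff telephone, and 13.2 deliberately combines observation, spontaneous reports and questioning. An event on day 29 is reportable and recordable as the plan stands. The 2 days is also only nominal: drug termination is not defined, no window is given, and a call dated from a week-12 visit held after the last dose could fall on or after day 30. The days in question are off drug, four weeks after stopping, and no analysis decision depends on them. Patients with persisting DMO are offered NHS standard care, so further clinic contact is likely. The 28 days in 8.4 is advice to early stoppers and does not shorten 13.7. Finally, the SAP's past-tense remark about week 16 suggests that treatment is over, so rescheduling may be moot, and SAP Table 1 already shows AE collection ending at the 4-week call.

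Much of this stands and limits the size of the point. Passive capture does continue to day 30, and the exposure period itself is covered by AE checks at weeks 2, 4, 8 and 12. What it does not supply is a planned contact at or after day 30. Likely NHS attendance is not guaranteed by then, and the follow-up to resolution in 13.7 applies to related and serious events already identified; it does not find new ones. The advice in 8.4 remains two days shorter than the reporting period whatever the window for the call. SAP Table 1 shows when the last contact is due, but neither it nor SAP 7.5 says that collection is passive from then to day 30.

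**Conclusion.** The concern holds and is minor. Planned active AE questioning nominally ends 2 days before the reporting period does. The 2-day figure assumes that drug termination means the last dose and that the call is made on its nominal day; a call on day 30 or later would leave no gap. The mismatch between 28 and 30 days in the text does not depend on either assumption. Because contraception and pregnancy reporting also run to 30 days, the 4-week call and the 28 days in 8.4 are the figures out of line. Few AEs are likely to be missed, and no efficacy result is affected.

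**What to change.** If calls are still to be made, schedule the existing final telephone check on or after day 30 from the last dose in Protocol 8.4, 10.10 and Table 2 and in SAP Table 1, and change 28 to 30 days in the Protocol 8.4 advice. The same call would then also fall at or after the end of the pregnancy reporting period. The cost is a call two days later and a minor wording amendment, which may need approval under Protocol 16.9. It adds no contact for patients.

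If the calls have already been made, leave the schedule alone. State in SAP 7.5 and in the report that AEs were actively asked about up to each patient's actual final contact date and collected passively from then to day 30. That costs one sentence in each document.
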